**STUDY ASSESSMENTS:**

**Table 1: Schedule of Activities**

Activity	Screening 	Cycle (28 days)			End of Treatment Visit 	Follow Up Visit 	Follow Up Contact 
		D1 (± 2d)	D15 (± 2d) 	D25 (± 5d) 			
ICF, Inclusion/exclusion criteria evaluation, HIPAA form	X						
Medical History 	X						
Concomitant meds and AE assessment 		X (assessed at each study visit and as clinically needed)					
Complete physical examination, including vital signs (heart rate, blood pressure, temperature)	X 				X		
Weight	X	X			X		
Height	X						
ECOG performance status	X 	X			X		
Symptom based physical examination		X	X 	X			
Pregnancy test 	X 	X 			X		
Serum chemistry 	X 	X 	X		X		
Hematology 	X 	X 	X	X	X	X 	
Coagulation 	X 				X		
Perform bone marrow aspirate for disease assessment, cytogenetic assessment and bone marrow biomarkers, including CXCR4/2 ratio 	X 			X 	X	X 	
Completion of MPN- SAF TSS 	X			X	X	X 	
Record the number of RBC, whole blood and platelet transfusions 	X	X		X	X	X 	
Blood sample for NGS oncogene panel sequencing including KRAS, NRAS 	X				X		
Plasma and serum samples for biomarkers 		X		X			
Tipifarnib administration 		X	X	X 			

Drug accountability		X 			X		
Buccal swabs 	X						
Collection of survival and anticancer treatment information							X

1. Screening evaluations will be completed within 4 weeks (28 days) of Cycle 1 Day 1. Evaluations performed as part of the standard of care within 28 days of dosing but prior to consent do not need to be repeated. By signing the consent form, study subjects agree to the collection of standard of care health information. The following screening evaluations should be completed within 14 days of Cycle 1 Day 1: complete physical exam, ECOG performance status, serum chemistry, hematology and coagulation. Female subjects must have a negative serum or urine pregnancy test within 72 hours prior to start of study medication (Cycle 1 Day 1).

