12. During screening, hematology, serum chemistry and coagulation must be done within 14 days prior to first administration of study drug on Day 1 of Cycle 1. Hematology and serum chemistry laboratory tests do not need to be repeated on Cycle 1 Day 1 if the screening laboratory tests were conducted within 72 hours prior to the first dose of tipifarnib. Fasting for laboratory testing is not required. Laboratory tests may need to be conducted on additional time points if deemed necessary by the Investigator. Samples will be analyzed locally at the clinical site or its reference laboratory. Laboratory assessments may be repeated if values are borderline to inclusion level or may change due to best supportive care measures. Hematology should include: hemoglobin, platelets, WBCs, neutrophils, neutrophil precursors, monocytes, lymphocytes and blasts. Serum chemistry should include: AST, ALT, total bilirubin, creatinine, potassium and calcium. Coagulation should include: PT/INR, APTT.
13. Laboratory tests do not need to be repeated on Cycle 1 Day 1 if the screening laboratory tests were conducted within 72 hours prior to the first dose of tipifarnib.
14. As part of the disease assessment at screening and at the Day 25 visit performed during Cycles 2, 4, 6 and 9, bone marrow evaluation will be performed. Thereafter, bone marrow evaluations will occur during disease assessments in accordance with institutional standard practice. If a CR or PR is observed on the bone marrow sample, a bone marrow aspirate must be repeated 1 month later, i.e. prior to the end of the next cycle. If the bone marrow aspiration results in an inadequate sample for disease assessment, a bone marrow biopsy should be performed. RNA samples for biomarker analyses will be taken at Screening and Cycle 2 only.
15. Samples for RT-PCR of CXCR4, CXCR2, and CXCL12, and gene expression profiling by RNASeq (PAXgene RNA tubes) will be provided at screening, C2D25 and EOT. A bone marrow sample for whole exome next generation DNA sequencing (NGS) of common myeloid mutations, including sequencing of KRAS and NRAS, will be provided at screening (PAXgene DNA tubes). Bone marrow aspirates will be collected as per institutional standard practice.
16. At the screening visit, record the number of red blood cell (RBC), whole blood and platelet transfusions for the four months prior to Cycle 1 Day 1; for all other visits, the number of transfusions should be recorded since the last study visit.

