# **11                        STUDY PROCEDURES**

## **11.1                    Screening and Baseline Assessments**

A signed Informed Consent Form (ICF) must be obtained before any study-specific screening evaluations are performed and should be documented in the subject's medical chart.

The following evaluations and procedures will be performed within 28 days prior to the first study drug administration (Cycle 1 Day 1). Any screening evaluation, including disease status, will need to be repeated if performed more than 28 days from Cycle 1 Day 1. Evaluations performed as part of the standard of care within 28 days of dosing but prior to consent, do not need to be repeated. By signing the consent form, the subject agrees to the collection of this health information.

- Obtain signed ICF and form for the HIPAA/Data Protection Act
- Record subject's medical history, including demographics, primary diagnosis and WHO classification, outcome and duration of response to prior cancer therapy and any ongoing AEs
- Record concomitant medications
- Record subject weight
- Record subject height

- Perform bone marrow aspirate for disease assessment, cytogenetic assessment and RNA bone marrow biomarker analysis.
- In MDS/MPN subjects, complete symptom assessment as per the myeloproliferative neoplasm symptom assessment form total symptom score (MPN-SAF TSS, Emmanuel 2012)
- Record the number of RBC, whole blood and platelet transfusions for the 4 months prior to Cycle 1 Day 1.
- Collection of buccal swabs. If swabs are not collected at screening for any reason, collection can be conducted at any time during the study.
- Blood sample for NGS oncogene panel sequencing including KRAS, NRAS. Subjects with known wild type KRAS, NRAS status can be enrolled in the study prior to receiving the outcome of the oncogene panel test; however, if wild type RAS status is not confirmed in the NGS panel test, the subject will be replaced and continuation of treatment should be discussed with the Sponsor.
- 

The following evaluations and procedures will be performed within 14 days prior to the first administration of study drug (Cycle 1 Day 1):

- Complete physical examination including vital signs (heart rate, blood pressure, temperature)
- Assess ECOG performance status.
- Perform hematology tests (hemoglobin, platelets, WBCs, neutrophils, neutrophil precursors, lymphocytes, monocytes and blasts)

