- Perform serum chemistry laboratory tests (AST, ALT, total bilirubin, creatinine, potassium and calcium). Subjects are not required to be fasting.
- Perform coagulation tests (APTT, PT/INR)

The following evaluations and procedures will be performed within 72 hours prior to the first administration of study drug (Cycle 1 Day 1):

- Perform urine or serum pregnancy test for females of child-bearing potential only

Laboratory assessments may be repeated if values are borderline to inclusion level or may change due to best supportive care measures.

If the subject meets all eligibility criteria after the screening visit(s), the study site will request an assigned subject number and treatment assignment from the Sponsor or designee.

## 11.2 Day 1 of Cycle 1

The following assessments will be conducted before the first dose of tipifarnib on Day 1 of Cycle 1:

- Record concomitant medications

- Assessment of AEs
- Record subject weight
- Assess ECOG performance status.
- Symptom based physical examination
- Perform serum chemistry laboratory tests (AST, ALT, total bilirubin, creatinine, potassium and calcium). Subjects are not required to be fasting. Serum chemistry tests do not need to be repeated on Cycle 1 Day 1 if the screening laboratory tests were conducted within 72 hours prior to the first dose of tipifarnib.
- Perform hematology tests (hemoglobin, platelets, WBCs, neutrophils, neutrophil precursors, lymphocytes, monocytes and blasts). Hematology tests do not need to be repeated on Cycle 1 Day 1 if the screening hematology tests were conducted within 72 hours prior to the first dose of tipifarnib.
- Record any RBC, whole blood and platelet transfusions that were received between the screening visit and Cycle 1 Day 1.
- Collect serum and plasma samples for biomarker evaluation

Tipifarnib should always be administered with a meal. For convenience, subjects may receive only one dose of tipifarnib on Cycle 1 Day 1, with subjects self-administering the first dose of tipifarnib with food in the evening. Subjects will continue to self-administer tipifarnib twice a day (approximately every 12 hours, same time every morning and evening, with a meal). The interval between dosing should not be less than 6 hours.

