### **11.3 Day 1 ( $\pm$ 2 days) of Cycle 2 and every cycle thereafter**

Subjects will self-administer their morning dose of tipifarnib with food prior to the following procedures:

- Record concomitant medications
- Assessment of AEs
- Record subject weight
- Assess ECOG performance status.
- Symptom based physical examination
- Perform urine or serum pregnancy test for females of child-bearing potential only
- Perform serum chemistry laboratory tests (AST, ALT, total bilirubin, creatinine, potassium and calcium). Subjects are not required to be fasting. If clinically indicated, serum chemistry tests may be repeated more frequently.
- Perform hematology tests (hemoglobin, platelets, WBCs, neutrophils, neutrophil precursors, lymphocytes, monocytes and blasts). If clinically indicated, hematology tests may be repeated more frequently.

- Record any RBC, whole blood and platelet transfusions that were received since the last study visit.
- Conduct a drug accountability on the returned empty bottles and unused medications.

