#### **11.4 Day 15 ( $\pm$ 2 days) of Cycle 1 and Cycle 2**

Subjects will self-administer their morning dose of tipifarnib with food prior to the following procedures:

- Record concomitant medications
- Assessment of AEs
- Symptom based physical examination
- Perform serum chemistry laboratory tests (AST, ALT, total bilirubin, creatinine, potassium and calcium). Subjects are not required to be fasting. If clinically indicated, serum chemistry tests may be repeated more frequently.
- Perform hematology tests (hemoglobin, platelets, WBCs, neutrophils, neutrophil precursors, lymphocytes, monocytes and blasts). If clinically indicated, hematology tests may be repeated more frequently.

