## **11.7 Post Treatment Follow up**

### **11.7.1 Follow-up Visit: Subjects who Terminate Treatment for Reasons other than Death or Disease Progression**

Subjects who terminated treatment for reasons other than death or disease progression will be assessed at regular intervals for disease progression and leukemic transformation.

The assessments to be conducted at each monthly visit are:

- Perform hematology tests (hemoglobin, platelets, WBCs, neutrophils, neutrophil precursors, lymphocytes, monocytes and blasts)

The assessments to be conducted at each approximately every 2 months through the first 6 months from the start of the subject's participation in this study and every approximately 12 weeks thereafter are:

- Perform bone marrow aspirate for disease assessment and cytogenetic assessment as part of the assessments conducted during the first 9 months from the start of the subject's participation in the study. Thereafter, bone marrow evaluations will occur during disease assessments in accordance with institutional standard practice. If the bone marrow aspirate is inadequate, a bone marrow biopsy should be performed. If on this bone marrow sample, a CR or PR is observed, a bone marrow aspirate with cytogenetic assessment must be repeated 1 month later.
- In MDS/MPN subjects, Complete symptom assessment as per the MPN-SAF TSS
- Record any RBC, whole blood and platelet transfusions that were received since the last study visit.

Assessments of AEs and concomitant medications may also be conducted if AEs were not resolved at the time of the End of Treatment visit.

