10.1 Definition of endpoints

Disease assessments other than bone marrow (hematology and quality of life evaluations) will be performed at screening, and at the Day 25 visit (\pm 5 days) performed during Cycles 2, 4, 6, 9 and every approximately 12 weeks thereafter (Cycles 9, 12, 15, etc.), at the End of Treatment visit and during Follow Up. Bone marrow evaluation will be performed as part of the disease assessment at screening and at the Day 25 visit (\pm 5 days) performed during Cycles 2, 4, 6 and 9. Thereafter, bone marrow evaluations will occur during disease assessments in accordance with institutional standard practice. Hematologic assessments, including peripheral blood evaluations and review of transfusion requirements, will be performed at screening and at least

monthly until disease progression. Additional disease or hematologic assessments may be conducted if deemed necessary by the Investigator.

For subjects with CMMI and MDS/MPN, determination of disease response will be performed by the Investigator according to the MDS/MPN IWG criteria (Protocol Table 9 and 10); Objective Response (OR) is achieved if the investigator indicates complete response, complete cytogenetic remission, partial remission, marrow response, or clinical benefit.

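### The transfusion look-back stops at the preceding study visit, but Day 15 and monthly follow-up visits record no transfusions, so on a literal reading the post-baseline count has gaps that the baseline count does not

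*Protocol*

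**What the plan says.** **Where transfusions are recorded.** The Table 1 row "Record the number of RBC, whole blood and platelet transfusions" is marked at screening, Day 1, Day 25, End of Treatment and the follow-up visit. The Day 15 cell is empty.

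**How far back each record reaches.** Footnote 16 sets the rule after screening: "for all other visits, the number of transfusions should be recorded since the last study visit". Section 11.3 (Day 1 of Cycle 2 onward) says: "Record any RBC, whole blood and platelet transfusions that were received since the last study visit". Sections 11.5 (Day 25), 11.6 (End of Treatment) and 11.7.1 (follow-up) repeat it.

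**Day 15.** Footnote 23 places this visit in Cycles 1 and 2 only. Section 11.4 lists concomitant medications, adverse events, a symptom-based examination, chemistry and hematology. It has no transfusion item.

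**Follow-up after stopping for reasons other than death or progression.** In section 11.7.1 the list introduced by "The assessments to be conducted at each monthly visit are" holds hematology only. Transfusions appear only in the list for the assessments due about every 2 months, later about every 12 weeks.

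**Baseline.** Section 11.1 has: "Record the number of RBC, whole blood and platelet transfusions for the 4 months prior to Cycle 1 Day 1". Section 11.2 closes the remaining interval: "Record any RBC, whole blood and platelet transfusions that were received between the screening visit and Cycle 1 Day 1".

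**Frequency of review.** SAP 10.1 states: "Hematologic assessments, including peripheral blood evaluations and review of transfusion requirements, will be performed at screening and at least" once a month, up to progression. Protocol 8.1 and 10.1 require the same.

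**The concern.** A look-back to the preceding visit gives a complete count only if every visit takes the count. Here Day 15 resets the look-back without recording anything. The monthly follow-up visits do the same.

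The asymmetry runs one way. Baseline is continuous up to the first dose, while the record after it can only miss events. A subject whose transfusion need has not changed can therefore show fewer transfusions on treatment than before it.

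The record matters because Protocol 10.1 places the review of transfusion needs under efficacy variables, and SAP 10.1 mentions it in the endpoint definitions. SAP 10.1 also counts clinical benefit as an objective response. There is no control arm, and a single response among seven subjects opens Stage 2 of a cohort (Protocol 8.1). An incomplete transfusion history is worth avoiding in that setting, even though the documents do not show how it would enter a response call.

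**Working it through.** The documents give no figure for transfusion capture, so there is none to reproduce. The check is interval arithmetic on the schedule.

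**Inputs (Table 1; sections 11.2 to 11.5).** 28-day cycles; Day 1 ±2 days, Day 15 ±2 days, Day 25 ±5 days. Cycle 1 Day 1 is fixed as study day 1. The first post-baseline disease assessment is Cycle 2 Day 25.

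**Nominal schedule, literal reading**

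| Visit | Study day | Transfusion item? | Interval covered |
|---|---|---|---|
| Cycle 1 Day 1 | 1 | yes | screening to day 1 |
| Cycle 1 Day 15 | 15 | no | none |
| Cycle 2 Day 1 | 29 | yes | day 15 to 29 |
| Cycle 2 Day 15 | 43 | no | none |
| Cycle 2 Day 25 | 53 | yes | day 43 to 53 |

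Uncovered = (15 − 1) + (43 − 29) = 14 + 14 = 28 days. Total = 53 − 1 = 52 days. Share = 28/52 = 53.8%.

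**Across the visit windows**

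- Smallest share: visits on days 13, 31, 41 and 58. Uncovered = 12 + 10 = 22; total = 57; 22/57 = 38.6%.
- Largest share: visits on days 17, 27, 45 and 48. Uncovered = 16 + 18 = 34; total = 47; 34/47 = 72.3%.

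**Later assessments.** No Day 15 visit follows Cycle 2, so the 28 days do not grow while the subject stays on treatment.

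- Cycle 4 Day 25 is day 3 × 28 + 25 = 109: 28/108 = 25.9%.
- Cycle 6 Day 25 is day 5 × 28 + 25 = 165: 28/164 = 17.1%.

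**Off-treatment follow-up, taking monthly visits as about 4 weeks apart**

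- 2-monthly phase: the look-back reaches only the intervening monthly visit, so about 1 month of 2 is uncovered (one-half).
- 12-weekly phase: the look-back covers the last 4 of 12 weeks, so 8/12 is uncovered (two-thirds).

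This gap is separate from the 54%. It adds to the period before the first assessment only for a subject who stops treatment before that assessment.

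**From days to transfusions.** This step needs an assumption, because the documents give no transfusion rate. At a constant rate, the expected recorded count up to Cycle 2 Day 25 would be 24/52 = 46% of the true count, with a range of 13/47 = 28% to 35/57 = 61% across the windows. If the rate changes over the first two cycles, the share of days is not the share of transfusions.

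**After the fix.** With each record reaching back to the previous transfusion record, uncovered time from Cycle 1 Day 1 to Cycle 2 Day 25 is 0 of 52 days.

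**The case against.** **Other routes require capture.** Protocol 9.11 names transfusions as supportive care and requires added concomitant therapy to be entered in the CRF. Concomitant medications are recorded at Day 15. Section 14.2 requires transfusion dates and numbers in the subject file, whatever the visit. Protocol 8.1 and 10.1 require a review of transfusion needs at least monthly.

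This stands against any claim that the events are lost, but it does not complete the transfusion count:

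- Section 9.11 asks for name, dose, duration and indication of a drug, not a number of transfusions, and SAP 9.2 and 9.3 report medications and transfusions separately.
- In follow-up, concomitant medications are reviewed only optionally, when adverse events are unresolved (section 11.7.1).
- The subject file is site source. It makes back-fill possible but does not fill the transfusion record.
- On treatment, the scheduled occasions for the monthly review are the same Day 1 and Day 25 records with the short look-back. In follow-up, the monthly visit does not include transfusions at all.

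**A benign reading exists.** Because footnote 16 governs one row of Table 1, the last visit could be taken to mean the last visit at which that row was completed. The chain would then be continuous. Some sites may read it this way, but the text does not say so, and sites that differ would produce counts that are not comparable.

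**The effect on response is not shown.** A reader might infer that unchanged transfusion need is being scored as response and that the objective response rate is inflated. The documents do not support that. SAP 9.3 lists transfusions without summarizing them, SAP 10.1 leaves response to the investigator, who holds the subject file, and the response criteria table is not in the available text. This part of the objection stands in full.

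**Conclusion.** The gap in the stated rule is real. Read literally, 28 of 52 nominal days before the first disease assessment (54%; 39% to 72% across visit windows) fall outside every transfusion look-back, against a gap-free baseline. The on-treatment share falls to 26% by Cycle 4 Day 25 and 17% by Cycle 6 Day 25. About one-half to two-thirds of off-treatment follow-up is also uncovered, and there the schedule contradicts the monthly review requirement.

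These are shares of calendar time. They rest on the literal reading of the look-back and, for follow-up, on visits about 4 weeks apart. A reader might infer that about half of all early transfusions go unrecorded. That does not follow: it would need a constant transfusion rate and the failure of the concomitant-therapy and subject-file routes.

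The supported conclusion is narrower: the transfusion count can be too low relative to baseline, by an amount that the documents do not let one state, and with an effect on the objective response rate that cannot be quantified. The passages should be reconciled, because the record belongs to the efficacy variables of a single-arm trial and completing it costs little.

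**What to change.** - In footnote 16 and sections 11.3, 11.5, 11.6 and 11.7.1, define the look-back as running from the last transfusion record instead of the last visit.
- Add the transfusion item to Day 15 (Table 1 and section 11.4) and to the monthly follow-up visits (Table 1 and section 11.7.1), so that the schedule meets the monthly review requirement in Protocol 8.1 and 10.1 and SAP 10.1.
- For subjects already treated, query the uncovered intervals and back-fill them from the subject file, which section 14.2 requires to hold transfusion dates and numbers.

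The cost is a wording change, one more data-entry item at existing visits and a short round of queries. No visit, sample or procedure is added.

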## 4 ABBREVIATIONS

AE	Adverse event
ALT	Alanine Aminotransferase
AML	Acute myeloid leukemia
ANC	Absolute neutrophil count
APTT	Activated partial thromboplastin time
AST	Aspartate Aminotransferase
bid	Twice a day
BSC	Best supportive care
CMML	Chronic myelomonocytic leukemia
CR	Complete response
CRp	Complete response with incomplete platelet count recovery
CRF	Case report form
CTEP	Cancer therapy evaluation program
CYP450	Cytochrome P450
DLT	Dose limiting toxicity
ECG	Electrocardiogram
ECOG	Eastern cooperative oncology group
FACS	Fluorescence-activated cell sorting
FAS	Full analysis set
GCP	Good Clinical Practice
HI	Hematological improvement
HIPAA	Health Insurance Portability and Accountability Act
HIV	Human immunodeficiency virus
HLA	Human leukocyte antigen
ICF	Informed consent form
ICH	International Conference on Harmonization
IEC	Independent Ethics Committee
IP	Investigational product
IRB	Institutional Review Board
IV	Intravenous
IWG	International Working Group
JMML	Juvenile myelomonocytic leukemia
KIR	Killer cell Immunoglobulin-like receptor
LDH	Lactic dehydrogenase
MDS	Myelodysplastic syndromes
MDS	Myelodysplastic syndromes
MDS/MPN IWG	Myelodysplastic syndromes/Myeloproliferative neoplasms International Working Group
MPN	Myeloproliferative neoplasm
MPN-SAF TSS	Myeloproliferative neoplasm symptom assessment form total symptom score
MTD	Maximum tolerated dose
N	Sample size
NCI	National Cancer Institute
NCI CTCAE	National Cancer Institute Common Terminology Criteria for Adverse Events
NGS	Next generation sequencing
ORR	Overall response rate
PDGFR	Platelet derived growth factor receptor
PR	Partial response
PFS	Progression free survival
PoS	Probability of meeting success criteria
PPS	Per protocol set
PT/INR	Prothrombin time/international normalized ratio
RBC	Red blood cell
SAE	Serious adverse event
SAP	Statistical analysis plan

SGOT	Serum glutamic oxaloacetic transaminase
SGPT	Serum glutamic pyruvic transaminase
SUSAR	Suspected Unexpected Serious Adverse Reactions
TEAE	Treatment-emergent adverse event
ULN	Upper limit of normal
US	United States
WBC	White blood cell
WHO	World health organization

